1. Title: Evaluation of Fatigue in Short-Haul Operations Across Multiple Airlines

2. Organizations and Study Location(s): The research described will be performed by investigators at NASA Ames Research Center (ARC) in collaboration with researchers at the Civil Aerospace Medical Institute (CAMI), Washington State University (WSU), and Brigham and Women's Hospital (BWH). Due to the nature of the project, field data will be collected throughout the United States (US).

3. Investigator:

[name] MPH
NASA Ames Research Center
Human Systems Integration Division
[name]
[name]
[contact]
[contact]
Email: [contact]

Co-Investigators:

[name]
San José State University
NASA Ames Research Center
Human Systems Integration Division
[name]
[name]
Email: [contact]

[name], MA
NASA Ames Research Center
Human Systems Integration Division
[name]
[name]
Email: [contact]

Collaborators:

[name]
FAA Aviation Safety
Civil Aerospace Medical Institute (CAMI)
[name]
Email: [contact]

[name]
FAA Aviation Safety
Civil Aerospace Medical Institute (CAMI)
[name]
Email: [contact]

[name], MS, PhD
Washington State University (WSU)

Occupational Sleep Medicine Group

Email: [contact]

[name]

Brigham & Women's Hospital

Harvard Medical School

Division of Sleep Medicine

[name]

Email: [contact]

[name]

Senior Manager, Fatigue Risk Management

American Airlines

[name]

Email: [contact]

Fatigue Countermeasures Laboratory Study Staff:

[name] (SJSU Research Foundation)

[name] (NASA)

[name] (SJSU Research Foundation)

[name] (NASA)

[name] (SJSU Research Foundation)

[name] (NASA)

[name] (Menlo College)

[name] (SJSU Research Foundation)

[name] (SJSU Research Foundation)

[name] (SJSU Research Foundation)

WSU Research Team:

[name]

[name]

[name]

AA Research Team:

[name]

4. Purpose

This research is being conducted as a component of a Reimbursable Interagency Agreement between NASA and CAMI (IAA No. SAA2-403611). The purpose of the present study is to collect objective and subjective measures of sleep, sleepiness, performance, and workload that can be used to assess fatigue levels of short-haul pilots during normal operations.

5. Background

Aviation regulation and safety oversight is in an era of performance-based risk management. Research is ongoing to understand the role fatigue plays in degraded human performance during various types of

operations within the aviation system. As part of this process, the Federal Aviation Administration (FAA) proposed duty limits and rest requirements which went into effect in 2014 (Code of Federal Regulations [14 CFR] Part 117, 2012). A study of fatigue in short-haul operations under these regulations is yet to be conducted. Recently, the FAA proposed the need for research to evaluate fatigue within these regulations in short-haul operations.

Determinants of Alertness and Performance in Short-Haul Aviation Operations

There has been a great deal of research to understand the influence of factors such as circadian misalignment induced by jet lag during long-haul flights on pilot fatigue and performance, but comparatively fewer studies have been conducted to evaluate fatigue and performance among pilots during short-haul operations. There are several factors that have the potential to reduce alertness and performance among airline pilots during short-haul operations, including time of day, time awake, workload, and consecutive work shifts. Each of these factors can influence a pilot's fatigue and performance, and in combination, these factors have the potential to cause severe performance impairment.

Time of Day. The circadian rhythm promotes waking during the biological day and sleep at night. When individuals who are normally awake during the day and sleep at night have to engage in night work, the sleep drive is strongest and performance is worst during the hours of 0200 to 0559, a time that has been dubbed the Window of Circadian Low (WOCL; Scientific Principles for Fatigue Management, 2015). Prior studies confirm that micro-sleeps and fatigue ratings are highest during night flights (Samel et al., 1997), whereas performance is relatively stable during short-haul flights that occur during the day when the circadian rhythm is strongly promoting wakefulness (Flynn-Evans et al., 2018).

Start Time of Duty and Time Awake. The start time and time awake prior to a flight can also influence an individual's ability to obtain adequate sleep and maintain subsequent performance. Consecutive early work start times can lead to WOCL encroachments and lower quality sleep (Roach et al., 2012; Flynn-Evans et al., 2018), while later report times could mean pilots may wake several hours prior to their actual duty, increasing time awake before performing critical tasks (Rosekind et al., 1994; Samel et al., 1997; Gander et al., 1998; Caldwell et al., 2006; Vejvoda et al., 2014). Indeed, short-haul pilots who start work in the morning after 0900 have been shown to achieve more sleep (Roach et al., 2012; Flynn-Evans et al., 2018).

Flight Segments. Workload can also influence a pilot's fatigue level. Several studies have demonstrated that flying three or more flight segments in a single duty day is associated with increased subjective ratings of fatigue and poorer performance (Bourgeois-Bougrine et al., 2003; Powell et al., 2007; Honn et al., 2016).

Consecutive Operations. Several studies have demonstrated that working consecutive days is associated with poorer performance. For example, Flynn-Evans et al. (2018) found that pilots performed worse with each consecutive day of flying when scheduled for early starts, long midday flights, and late finishing daytime flights.

Preliminary Data: Focus Group Study

In order to identify fatigue factors of greatest importance to study, we conducted a series of focus groups across four major commercial passenger airlines in the United States. This study revealed several

operations that pilots identified as fatiguing (Table 1). We combined these themes into six over-arching categories including: circadian disruption, high workload, rest opportunity, schedule changes, regulations, and long sits. While categories provide a useful summarization of the overall content, the value of the qualitative approach is the resolution of data at theme and code level. Therefore, core *themes* and CODES contributing to these categories are described below.

Table 1. Themes ranked by frequency of codes within each theme.

Theme	N	%
Circadian switches	171	10.5
Rest duration (layover)	153	9.4
High workload / Hassle factors	151	9.3
Number of flights	121	7.4
FAR 117 issues	93	5.7
Long sits	85	5.2
Redeyes	83	5.1
Unpredictability	79	4.9
Aircraft & crew swaps	73	4.5
Rest timing	73	4.5
Out-of-hours work	68	4.2
Early duties	64	3.9
Short turn time	53	3.3
Length of duty	46	2.8
Rest quality	45	2.8
Schedule design	38	2.3
Trip length	37	2.3
Late duties	25	1.5
Fatigue calls	24	1.5
Length of flights	20	1.2
Rest - Circadian disruption	20	1.2
Deadhead	14	0.9
Total	1625*	

Note: * = total includes codes that did not fit a defined theme. Percentage column reflects the proportion of all codes counted within each theme.

Circadian disruption. This category includes all themes related to inconsistent schedules (*Circadian switches*), duties outside of daytime hours (*Redeyes, Early duties, Late duties, Out-of-hours work*), rest opportunities during the day (*Rest timing*), and rest breaks that involve a circadian switch between duties (*Rest – circadian disruption*).

The most common theme identified overall, *Circadian switches*, refers to changes in duty start times within a trip, for example switching from an early start time to a late start time. This theme was made up of codes including: CIRCADIAN SWAPS (34% of codes in this theme), INCONSISTENT DUTY TIMES

(25%), and SWITCHING TIME ZONES (18%). SWITCHING TIME ZONES refers to the sentiment that while a schedule may look consistent based on local departure times, similar local start times in different time zones could lead to circadian shifts of up to three hours. For example, a west coast-based pilot may start day 1 of a trip at 0600h on Pacific Time (PT) and then have a 0600h report time on day 2 on Eastern Time (ET), which is effectively 0300h PT.

High workload. This category includes all themes related to increased workload such as *High workload & hassle factors*, *Number of flights*, *Aircraft & crew swaps*, *Short turn times*, and *Length of flights*. The third most common theme identified overall was *High workload & hassle factors*, which refers to a collection of operational challenges contributing to fatigue. Often these factors add to overall workload through increased mental effort or creating time pressure and not allowing for mental recovery during or between flights. Some factors also extend duty times, leading to extended time awake and reduced rest opportunity. This theme was made up of codes including: WEATHER (30%), MAINTENANCE (19%), GROUND OPS (18%), and BUSY AIRPORTS/REGIONS (14%).

This category also includes the fourth most common theme, *Number of flights*. This theme refers to the number of flights within a duty period. While long-haul operations typically only involve one flight within a duty period, short-haul operations typically include two or more flights within a duty period. Most responses within this theme (41%) indicated that duty periods with more than four flights were considered fatiguing. However, approximately one-third (36%) of the codes in this theme indicated a preference for duty periods with two or fewer flights in order to avoid fatigue, with a quarter (23%) suggesting that any duty with more than one flight is automatically fatiguing due to the nature of the operations.

Rest opportunity. This category includes themes related to rest opportunities independent from the timing of those opportunities (see **Circadian disruption** for *Rest timing*) including *Rest Duration (Layover)* and *Rest quality*. *Rest quality* covered codes related to hotel sleep environment (e.g., noise, temperature). *Rest duration (layover)* was the second most common theme and refers to insufficient rest opportunity between duties. This theme was made up of codes including: SHORT REST (42%), and PERSONAL TIME (30%). SHORT REST referred to comments indicating that the FAR 117 minimum rest requirement of 10 hours is too short for sufficient sleep opportunity. PERSONAL TIME includes comments regarding the need for time to eat, exercise, wind down, and prepare for the next duty within the allocated rest period. In a short rest period, often there is not enough time for all these factors, leading to skipping important daily needs and/or reducing the amount of time available for sleep.

Schedule changes. This category emerged from the theme, *Unpredictability*, which covered codes such as SCHEDULE CHANGES (43%), PLANNED VS OPS (29%, planned schedules being different to operational reality), and EXTENSIONS and DIVERSIONS (28%). Schedule changes affected fatigue by extending flight or duty time, adding workload, and/or changing the timing of duty and rest opportunities.

Regulations. This category includes the fifth most common theme, *FAR 117 issues*, as well as *Fatigue Calls*. *FAR 117 issues* refers to comments from participants regarding the regulations (FAR 117) dictating the current flight, duty, and rest time requirements and how they are implemented. Thirty-seven percent of the codes in this theme related to the use of FAR regulations by airlines as goals or targets, rather than limits. A further 24% recommended revisions to the regulations in order to effectively manage fatigue. Some participants felt that the scheduling software used to create pairings lacked human insight into obviously fatiguing duties and trips. With regard to *Fatigue Calls*, participants

commented on barriers to submitting fatigue calls (BARRIERS, 42%) such as lack of pay protection and the drive to “get the job done”. A third of codes in this theme (RESPONSIBILITY, 33%) reflected the pilots’ disagreement with the fatigue call system putting the responsibility on the pilot to call out fatigued, and felt that more responsibility should lie with the airline to provide less fatiguing schedules.

Long sits. This category emerged from the theme, *Long Sits*, which in turn was derived from the code LONG SITS. Sit time refers to the time between flights within a duty during which the pilot has to wait in the airport until the next flight. The general consensus among participants was that a long sit would be defined as a sit time greater than 2 hours. The concept of long sits was so prevalent in the transcripts, that despite not being merged with any other codes, it was the sixth most common theme. The concept was also unrelated to the other themes, hence warranting its own category in order to capture this unique concept.

It is difficult to study the impact of so many factors on fatigue because the series of flights that pilots are scheduled for, known as a trip, can include factors that make data aggregation difficult without an enormous sample size. As a result, it is necessary to collect data on targeted operations in order to evaluate the impact of the most disruptive factors on fatigue. Hence, our primary aim is to compare sleep, sleepiness, performance, and workload during trips *with* circadian disruption to trips *without* circadian disruption. We will collect observational data on the other factors that were identified in the focus groups in order to help inform future research in those areas. We will study participants during their normal scheduled operations.

6. Why Human Research is Required

Human research is required because there are no other reliable, efficient, and cost-effective methods for obtaining such information from animal or modeling sources. Only performance by humans is possible or relevant.

7. Conflict of Interest

Do any of the participating study investigators or other research personnel (or their immediate family/significant other) have a financial and/or intellectual property interest in the sponsor or products used with this project?

____ Yes No

8. Plan of Study

8.1 Protocol Overview

Scientific Merit. Please see attached ARC476 for scientific review and approval.

Specific Aims. The goal of this study is to provide insight into the influence of trips including circadian disruption on pilot cognitive performance, fatigue, sleepiness, sleep, and workload during short-haul operations across multiple airlines.

Hypotheses.

We aim to study pilots completing trips that include circadian disruption compared to trips that do not include circadian disruption.

- We hypothesize that cognitive performance, fatigue, sleepiness, and sleep outcomes will be worse during circadian disrupted trips compared to trips that do not involve circadian disruption.

Primary Outcome Measures.

Objective cognitive performance will be measured by the **psychomotor vigilance task (PVT)**, a simple reaction time task with outcome measures including mean reaction time, response speed (1/reaction time) and number of lapses (reaction time >500 ms). PVT performance will be measured at, or near, the timing of top of descent (TOD) during each flight.

Statistical Analyses.

The following factors will be also considered for inclusion in the analysis:

- **Schedule features:** flight duration, duty duration, duty start and finish times
- **Individual factors:** age, experience, chronotype (as measured by the morningness-eveningness questionnaire), sleep need
- **Sleep:** sleep duration, sleep loss, sleep start and finish times (all measured by the actiwatch)
- **Fatigue/alertness:** pre- and post-sleep and on-duty fatigue and alertness ratings (as measured by subjective scales)
- **Workload:** hassle factors encountered during flights and NASA TLX

8.2 Equipment

The study will involve evaluating pilot sleep, sleepiness, performance, and workload among on-duty pilots. All devices are commercial, off-the-shelf products with no modifications and used as directed.

iPod. Participants will be issued an iPod Touch with a pre-loaded application (NASA PVT+) which includes a sleep diary, cognitive tests, and subjective scales (Figure 1). Using the NASA PVT+ App, measures will include PVT speed (1/reaction time) and lapses conducted at pre-flight, top of descent (TOD), post-flight, and on days off. Subjective fatigue ratings using the Samn-Perelli 7-point scale and sleepiness ratings using the 9-point Karolinska Sleepiness Scale at pre-flight, TOD, post-flight, and on days off will also be reported. At the end of each flight, participants will complete the NASA-TLX, hassle factors, and information about any fatigue countermeasures that they used. They will also capture information about the characteristics of the flight at the end of each Flight Duty Period (FDP). Prior to and at the end of the study, they will use the app to complete baseline questionnaires.

Actigraphy. Participants will wear a small wristwatch-like device (Actiwatch, Philips Respironics, Murrysville, PA, USA) on the wrist of their non-dominant arm (Figure 2). The actiwatch will be worn continuously throughout the study period including on days off. Actigraphy uses accelerometry and a light sensor to determine sleep and wake patterns and may be worn for several weeks at a time. It will provide us with objective sleep measures which can be compared and correlated with other measures recorded in the NASA PVT+ App.

Light and Temperature Sensor. Participants will wear a small (~1 square inch) light sensor clipped to their clothing in order to assess their lighting and ambient temperature exposure. This device can be placed on a bedside table during sleep. It can record light information for several weeks and does not require the user to interact with it in any way. The data obtained from this sensor will allow us to use the participant's pattern of light exposure to estimate circadian phase using a biomathematical model (Mohamed et al., 2021).

[figure not shown]

Figure 1. NASA PVT+ App screenshots

Figure 2. Actiwatch Spectrum Device

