Once consented, participants will be provided with instructions regarding the study procedures and equipment (i.e., an iPod with the NASA PVT+ application, an Actiwatch, and a light and temperature sensor). Equipment will be either be mailed to the participant or available for collection from a designated staff member. Participants will then complete a series of baseline questionnaires including a demographic questionnaire, performance questionnaires, a baseline exercise questionnaire, the Morningness/Eveningness Questionnaire (MEQ), the Epworth Sleepiness Scale (ESS), the Pittsburgh Sleep Quality Index (PSQI), the Insomnia Severity Index (ISI), and the NASA Task Load Index (TLX), using the NASA PVT+ app. Participants will also complete a practice sleep diary and a practice PVT in order to ensure that they understand the study procedures. Demographic information, including age, flight experience, living arrangements, and the results of the aforementioned questionnaires will be used as covariates in data analysis as each of these factors can influence sleep and performance.

Procedure

Participants will begin data collection 1-3 days prior to their trip departure (depending on the participant's availability and off-duty time between trips). Data will be collected using the NASA PVT+ App and the Actiwatch. Participants will begin wearing the Actiwatch and continue to wear it for the duration of the study period which will conclude up to 3 days following their return from their trip. They will make entries in the App reporting on their sleep periods at the beginning and end of each day, including days off. Participants will also have additional entries during flight duty periods.

A study staff member will check in (e.g., via phone call) regularly to remind the participant to complete the study tasks and to answer any additional questions.

Details are outlined below as well as summarized in Table 2 and Figure 3. Full details can be found in supplemental documents.

Return of equipment. Participants will be provided with either a return pre-paid box or instructions on where to return the equipment to a designated staff member. Data will be downloaded, cleared, and a study ID reset on each device before sending to another participant. Data collected on iPod and actiwatch devices will only be identified by an ID code. No identifying information will be collected during the study period.

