Morning Sleep Diary. At the beginning of each day, participants will complete a sleep diary within the NASA PVT+ App. Each entry will include: wake-up time, a rating of sleep quality (5 -point scale from Extremely Good to Extremely Poor), the Samn-Perelli (SP) and Karolinska Sleepiness Scale (KSS), the location of their sleep, the timing and duration of any awakenings during the sleep period, and any additional information (i.e., notes).

Evening Sleep Diary. At the end of each day (right before sleep), participants will use the App to report the time they are going to sleep, the location of their sleep (e.g., home, hotel), if they used any caffeine during the day (amount used), any naps during the day (including timing and duration), timing/type of meals, and timing/type of exercise. Participants will also complete the SP and KSS and have an opportunity to provide any additional information about the day if necessary.

Flight Duty Period Data Collection. On flight duty days, participants will have additional entries and tasks to complete within the NASA PVT+ App (i.e., pre-duty, during flight, post-flight, and post-duty). Pre-duty entries will include: flight information, layover information, commute information, caffeine intake, the SP and KSS, and the Psychomotor Vigilance Task (PVT). During their flight, they will complete the SP, KSS, and the PVT, at or near the timing of TOD. Post-flight entries will occur within one hour of landing and will include flight information, the NASA TLX, report of fatigue countermeasures used, and hassle factors experienced (e.g., weather, air traffic control issues, traffic), SP, KSS, and PVT (if needed). Post-duty entries will include: duty information, operational factors (e.g., delays, sit times), overall fatigue rating (visual analog scale), KSS, SP, and PVT. Participants will also complete both the morning and evening sleep diary entries on flight duty days. Additional questions in the evening sleep diary on duty days include: commute information (i.e., timing, duration, and type of travel).

Table 2. Timing of data collection (repeated for one circadian-disruption trip and one trip without circadian disruption)

	1-3 Off-duty Days	Each Day of the Trip	1-3 Off-duty Days
Morn/evening Sleep Diary	✓	✓	✓
Sleepiness/ Fatigue	✓	✓	✓
Performance	✓	✓	✓
Workload		✓	
Duty information		✓	

[figure not shown]

Figure 3. Timing of flight day data collection

Tests and Scales

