Sleep Quality rating. All sleep periods (including naps) will be rated for quality. The scale includes: 1 = extremely good, 2= good, 3 = average, 4= poor, 5 = extremely poor.

Psychomotor vigilance task (PVT). The PVT is a widely used sustained-attention, reaction-time task that measures the speed with which subjects respond to a visual stimulus. The PVT is a simple task where the subject taps the screen as soon as a visual stimulus appears. The stimulus appears randomly every few seconds during the 5-minute task.

The initial screen orients the subject to take the test in landscape mode with thumbs hovering over the screen for response (Figure 4).

Figure 4. Orientation screen shown prior to each PVT

At random intervals the counter starts running with the clock showing in the response box (Figure 5). Tapping the screen stops the counter, showing the reaction time, before the screen clears and readies for the next stimulus presentation. At the end of the test the screen will display DONE.

Figure 5. PVT screen showing response time (ms)

10. Practical Aspects of Safety and Ethical Conduct

This study is a minimal risk study. The risks associated with the protocol may differ from normal flying duties due to potential discomfort and inconvenience with wearing the actiwatch and completing tests with the PVT+ App. All participants are active-duty pilots with the appropriate clearances for flight duties. The actiwatch and iPod device housing the NASA PVT+ App are commercially available products. Participants will be informed that they may skip tests or stop the study at any time if they feel that their participation compromises flight safety. Given that the risks associated with this study are minimal, medical monitoring is not required.

11. Number, Source, and Pertinent Characteristics of Participants

Study Population. The study population does not include astronauts. All subjects will be medically qualified, active-duty flight crewmembers. Current American Airlines, United Airlines, Delta Airlines, and Southwest Airline pilots are eligible to participate in the study (pending review of other inclusion criteria, see below).

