- b. Trip without Circadian Disruption: This trip must not contain any duties that are scheduled to begin or end between 0000h and 0659h relative to home-base time.

Proposed Test Schedule. Pending final decisions by the airlines regarding flights to be studied, the study is expected to commence in the summer of 2022.

12. Benefits of Participation

The results of this study may inform our understanding of how fatigue emerges during typical short-haul operations in the United States.

13. Possible Inconveniences, Discomfort, Pain, and Risks to the Participants

The risks associated with the protocol may differ from normal flying duties as follows:

It is possible that crew could experience slight discomfort and inconvenience from wearing an Actiwatch such as skin irritation or a rash, although no more than from wearing a wristwatch. An Actiwatch is the size of a wristwatch and is designed to be worn for weeks at a time.

Participants will record their performance using a handheld device employing the data collection app. Some crew could experience a degree of discomfort and inconvenience as the result of having their performance recorded for an extended period. Participants could be distracted from their flight duties while taking the tests, however, they will be instructed to take the test prior to the TOD, while still in the cruise phase when distractions are minimal.

Participants may also be inconvenienced by having to complete sleep, fatigue, and workload ratings. However, it is estimated that study information will only take about a total of 30 min in a day to record, with each phase of collection (e.g., pre-duty, evening diary) taking no more than 7 minutes.

As the study data will be archived at each airline or airline partner, it is possible that individual ID-coded data could be viewed or used by airline personnel.

14. Measures Taken to Minimize Discomfort and Risks

If the participant finds the actiwatch uncomfortable, then the study staff will work with the participant to determine if a different band could be used to minimize discomfort. If no acceptable alternatives are identified, then the participant will be free to discontinue wearing the device, which may require withdrawal from the study.

Participants will also be instructed to stop taking the PVT if they need to attend to their flying duties.

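### Do the differing PVT schedules and the 30-minute daily burden estimate call for a change to the protocol?

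*Protocol*

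**What the plan says.** Section 8.2 (Equipment, iPod) introduces the app and says what its measures include: PVT speed and "lapses conducted at pre-flight, top of descent (TOD), post-flight, and on days off".

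Section 9 (Procedure) gives the duty-day detail. There is a PVT before duty, a PVT in flight close to TOD, and a PVT after duty. Between the last two comes a post-flight entry whose items end "SP, KSS, and PVT (if needed"; its timing is given as "Post-flight entries will occur within one hour of landing".

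For days off, the running text says "They will make entries in the App reporting on their sleep periods at the beginning and end of each day, including days off", and the diary descriptions name the two rating scales but no PVT. Table 2, captioned "Timing of data collection (repeated for one circadian-disruption trip and one trip without circadian disruption", nevertheless ticks performance for the off-duty days. The Procedure also refers the reader to Figure 3 and to supplemental documents for full details.

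Section 9 (Tests and Scales) fixes the length of the test: "The stimulus appears randomly every few seconds during the 5-minute task". Section 13 estimates that "study information will only take about a total of 30 min in a day to record", with no single phase above 7 minutes. Section 10 adds, with flight safety as the ground: "Participants will be informed that they may skip tests or stop the study at any time".

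Section 8.1 makes the PVT near TOD, on each flight, the primary outcome.

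**The concern.** Read side by side, Sections 8.2 and 9 give two lists of PVT occasions. The post-flight test has no condition in one and is conditional in the other. The post-duty test appears only in Section 9. Pre-flight in Section 8.2 could mean before every flight, whereas Section 9 has one test before duty. The text at hand gives no criterion for when a post-flight test is needed.

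If staff at four airlines worked from different readings, the secondary pre-flight, post-flight and off-duty PVT data would not be comparable, and that could not be repaired after collection. A post-landing test might also be taken as a stand-in for a missed TOD test, which would reach the primary measure.

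Finally, Section 5 says that short-haul duties usually have at least two flights, so several 5-minute tests must fit into about 30 minutes along with everything else. An understated burden could lead pilots to skip tests on the busiest days.

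**Working it through.** **Inputs.** PVT length 5 minutes (Section 9, Tests and Scales). Daily total about 30 minutes (Section 13). Let k be the number of flights in a duty period; the trip criteria in Section 11 set no upper limit on k.

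**The plan's own figure.** Section 13 gives no breakdown of the 30 minutes and does not tie it to a number of flights. It cannot be rebuilt, only compared with the PVT load.

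**PVT minutes per duty day.**

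- Section 9, no post-flight test: one pre-duty + k TOD + one post-duty = 5(k + 2).
- Section 9, a post-flight test after every flight: 5(2k + 2).
- Section 8.2, one pre-flight test per duty, with TOD and post-flight tests on each flight: 5(2k + 1).
- Section 8.2, all three tests on each flight: 5 × 3k = 15k.

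| Flights k | Section 9 minimum | Section 9 maximum | Section 8.2, one pre-flight test | Section 8.2, all per flight |
|---|---|---|---|---|
| 1 | 15 | 20 | 15 | 15 |
| 2 | 20 | 30 | 25 | 30 |
| 3 | 25 | 40 | 35 | 45 |
| 4 | 30 | 50 | 45 | 60 |
| 5 | 35 | 60 | 55 | 75 |

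On the Section 9 minimum, PVT time leaves 15 minutes for other entries at one flight, 10 at two and 5 at three. At four flights it takes the whole 30 minutes, and at five it exceeds it. On the fullest readings, 30 minutes is reached at two flights. The estimate is therefore plausible for days with one or two flights, tight at three, and too low from four.

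**Agreement by occasion.**

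| Occasion | Section 8.2 | Section 9 | Agree? |
|---|---|---|---|
| Before | pre-flight | pre-duty, once | looser wording |
| TOD | yes | yes, in flight | yes (also Section 8.1) |
| After flight | no condition | conditional | no |
| After duty | not listed | yes | Section 8.2 incomplete |
| Days off | yes | ticked in Table 2 | yes; time and number not in the text |

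Days off number 2 trips × (1 to 3 before + 1 to 3 after) = 4 to 12 per pilot. At an assumed one test a day that is 4 to 12 tests. The two places do not differ here, so this count does not measure a discrepancy.

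**Does any of it reach the primary measure?** Section 8.1 requires the test during the flight. Section 9 lists the in-flight and post-flight entries separately, and the latter comes after landing. An analyst selecting the in-flight tests has the primary data without needing to know when a post-flight test was called for.

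**The case for a change.** The strongest case for a change is that missed TOD tests are foreseeable. Pilots may skip tests (Section 10) and are told to stop the PVT when flying duties call (Section 14). The natural reading of a conditional post-flight test is then a make-up test, and the text at hand does not say whether it may count as TOD data. One sentence would settle that. Section 5 also mentions duties with more than four flights, where the word about in Section 13 cannot stretch to 35 minutes or more of PVT alone.

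Some of this stands. The post-flight wording does differ, Section 8.2 omits the post-duty test, and the burden estimate is low for days with four or more flights.

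The rest is weaker. Section 8.2 lists what the measures include and makes no claim to be complete, while Section 9 is the operative procedure. Figure 3, on flight-day timing, was lost when the PDF was read, and the supplements are not at hand, so it cannot be shown that the criterion is missing from the plan. All pilots use the same pre-loaded app and receive instructions on the procedures, which makes divergent schedules between airlines unlikely. Substituting a post-landing test would contradict the primary definition in Section 8.1, so an analyst following the Protocol would not do it.

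**Conclusion.** No change to the plan follows. What remains is a loose summary in Section 8.2 beside a fuller procedure in Section 9, and a rough burden estimate that is too low on days with four or more flights (30 minutes of PVT alone at four, 35 at five, on the smallest schedule). The TOD time point is the same in Sections 8.1, 8.2 and 9, so the primary comparison is unaffected. The sample size does not use the burden figure, and no analysis does. Aligning the wording would write down what staff and analysts would do in any case.

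This rests on three assumptions: that Section 9, with its figure and supplements, governs conduct; that in-flight and post-flight tests stay distinguishable in the app data, as their separate entries suggest; and that the 30 minutes was meant for a day with few flights. The Protocol gives no distribution of flights per duty, so how often the estimate is exceeded cannot be computed.
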